### **12.2.2. Patient Disposition**

A detailed description of patient disposition will be provided. It will include a summary of the number and percentage of patients entered into the study, enrolled in the study, and treated, as well as the number and percentage of patients completing the study or discontinuing (overall and by reason for discontinuation). A summary of all important protocol deviations will be provided.

### **12.2.3. Patient Characteristics**

Patient characteristics will include a summary of the following:

- patient demographics
- baseline disease characteristics
- preexisting conditions
- historical illness
- prior therapies
- concomitant drugs

Other patient characteristics will be summarized as deemed appropriate.

### **12.2.4. Concomitant Therapy**

Concomitant medications will be listed and may be summarized by the World Health Organization preferred name for the safety population.

### **12.2.5. Treatment Compliance**

The number of dose omissions, reductions, delays, number of cycles received, and dose intensity will be summarized for all treated patients per treatment arm. A summary of treatment compliance will be generated using information from drug accountability records and the patient diary. The number of tablets taken relative to the number expected to be taken will be summarized by cycle and treatment arm.

### **12.2.6. Primary Outcome and Methodology**

OS duration will be measured from the date of randomization to the date of death from any cause. For each patient who is not known to have died as of the data-inclusion cut-off date for a particular analysis, OS will be censored for that analysis at the date of last contact prior to the

data inclusion cut-off date. (Contacts considered in the determination of last contact date include AE date, lesion assessment date, visit date, and last known alive date.) A method of analysis for comparing OS between the treatment arms will use a Bayesian exponential-likelihood model with possibly a hierarchical random-effects distribution on treatment effects. The model incorporates historical data from 2 studies with a sorafenib plus placebo arm to augment the prospective control arm data. If the Bayesian posterior probability of superiority of the combination arm over the control arm (ie, HR <1) exceeds 0.84 under a strong prior, then it will be concluded that the combination arm is superior. The same analysis will be repeated using the weak prior. A similar Bayesian analysis will be carried out to provide 90% predictive intervals of the HR between the control arm and LY2157299 monotherapy.

### **12.2.7. Secondary Efficacy Analyses**

In addition to the above primary Bayesian analyses for OS, OS curves for each treatment arm will also be analyzed using the Kaplan-Meier product-limit method (Kaplan and Meier 1958). Two-sided, 95% CIs for median OS will be computed by the Brookmeyer and Crowley method (Brookmeyer and Crowley 1982). OS rates at 6 and 12 months will also be estimated using Kaplan-Meier estimates on the OS curve for each treatment arm. Associated 2-sided 95% CIs will also be calculated. Pairwise HRs along with 95% CIs between the 3 arms may be estimated using proportional hazards (PH) models. Additional exploratory analyses using PH models to control for other factors may be performed. Details will be specified in the statistical analysis plan.

TTP and PFS curves and TTP/PFS rates will be summarized (at 3 months, 6 months, 9 months, 12 months) using Kaplan-Meier estimates of the median survival times (including 95% CIs). Pairwise HRs along with 95% CIs between the 3 arms will also be provided. Additional exploratory analyses using PH models to control for other factors may be performed.

ORR based on RECIST version 1.1 and mRECIST will be estimated by dividing the total number of responders (complete response [CR] or partial response [PR]) by the number of who received at 1 dose of study treatment and had measureable disease at baseline. Exact 95% CIs by the method of Clopper and Pearson (Clopper and Pearson 1934) for each treatment arm will be provided.

### **12.2.8. Pharmacokinetic Analyses**

The plasma-concentration-versus-time data together with information on dosing and patient characteristics will be pooled and analyzed using a population PK analysis approach. Nonlinear mixed-effect modeling (NONMEM) will be used for the estimation of the population PK parameters of LY2157299. Sorafenib PK will be assessed against a published sorafenib population PK model.

All patients who have completed at least 2 days of sampling will be included in the PK analysis. LY2157299 PK will be modeled using NONMEM. These population parameters will describe the average dose-concentration relationship in the target population, the influence of fixed effects

(such as weight or age) on a PK parameter of interest, the interindividual variation in the PK parameter, and the residual variation in the observed concentration.

For the purposes of the JBAS clinical study report, plasma-concentration data will be illustrated graphically and summarized descriptively. If data is sufficient, then data from patients in this study will be modeled using the population approach for characterizing LY2157299 PK.

Exploratory PK/PD analyses will be conducted to identify the exposure-response (biomarker) relationship in this study. The PK and PK/PD analyses may be reported as separate stand-alone reports for this study. Additional analyses such as exposure-response using TTP and/or other appropriate clinical endpoints may be explored, if data warrant.

The version of any software used for the analysis will be documented, and the program will meet Lilly requirements for software validation. It is possible that other validated equivalent PK software programs may be used if appropriate, warranted, and approved by global PK management.

### **12.2.9. Pharmacodynamics Analyses**

PD parameters (eg, E-cadherin, pSMAD) will be analyzed using PD data from all patients who underwent PD assessments. The association between changes in PD parameters and clinical endpoints will be explored to determine their value as predictive biomarkers of drug effect on clinical outcome.

### **12.2.10. Health Outcome/Quality of Life Analyses**

Questionnaire compliance rates will be ascertained at each measurement time point until the end of study therapy including at discontinuation (Visit 801).

Summary descriptive statistics will be provided for the PRO data (ie, EORTC QLQ-30 and QLQ HCC 18) at each assessment. This summary will include mean, standard deviation, median, minimum, maximum, and change from baseline. Scores will be evaluated both in aggregate (that is, median values for each study arm at a given time point) and individually, in which each patient's score on study is evaluated relative to his/her baseline score. Time to symptomatic progression will also be evaluated, and longitudinal analyses, such as repeated measures, will be performed. Other exploratory longitudinal analyses may be performed.

### **12.2.11. Safety Analyses**

All safety summaries and analyses will be based upon the Safety Population as defined in Section [12.2.1](#).

Overall exposure to study drug, the numbers of patients completing each cycle, and the dose intensity will be summarized using descriptive statistics. The number of patients with any dose adjustment will be presented for entire treatment period as well as for each cycle. The number of patients with dose reductions, dose delays, or dose omissions will also be summarized, as will the reasons for dose adjustments.

An overall summary of AEs will be provided for AEs deemed by the investigator to be possibly related to study medication and will be repeated for events regardless of study drug causality. Incidence rates of these events will be compared between treatment arms using Fisher's exact test.

Safety analyses will include, but are not limited to, the following:

- all reported AEs, including seriousness, severity, and possible relationship to study drug, using CTCAE terminology and grades
- TEAEs, including seriousness, severity, and possible relationship to study drug, using CTCAE terminology and grades
- dose adjustments for any study therapy
- physical examination and other safety observations, including those specifically targeting the monitoring of cardiac safety
- laboratory measures

AE terms and severity grades will be assigned by the investigator using CTCAE version 4.0. MedDRA version 16 (or higher) will be used when reporting AEs by MedDRA terms. The MedDRA lower level term will be used in the treatment-emergent computation. A TEAE, defined as an event that first occurred or worsened in severity after baseline, will be summarized by SOC and by decreasing frequency of preferred term within SOC.

Laboratory and nonlaboratory CTCAEs will be summarized by CTCAE term and maximum CTCAE grade, including the total for maximum Grades 3 and 4. These summaries will be provided for events regardless of study drug causality and will be repeated for events deemed by the investigator to be possibly related to study medication.

Reasons for death will be summarized separately for on-therapy and within 30 days of last dose of study drug. SAEs will be summarized by preferred term.

Hospitalizations and transfusions during the study treatment period or during the 30-day safety follow-up period will be summarized by treatment group.

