**Test Product, Dosage, and Mode of Administration**

LY2157299 will be administered orally by daily dosing morning and evening (twice daily [BID]). The monotherapy dose will be 150 mg BID (300-mg daily dose) for 14 days, followed by 14 days with no study drug. The LY2157299 dose used in combination with sorafenib will be determined based on the results of the H9H-MC-JBAK (JBAK) study Part C (dose will either be 80 mg or 150 mg BID [160 mg or 300 mg daily dose]) for 14 days, followed by 14 days with no study drug.

LY2157299-matched placebo will be administered orally by daily dosing morning and evening (BID) for 14 days, followed by 14 days with no placebo.

Sorafenib will be administered orally by daily dosing morning and evening (BID) at 400 mg per dose (total dosage of 800 mg daily) for 28 days.

One cycle is defined as 28 days in all treatment arms.

**Planned Duration of Treatment Per Patient:** Patients will receive LY2157299 until their disease has progressed, the patient has died, or the patient discontinues for adverse events, investigator's judgment, or other reasons.

**Wash-out period:** none.

**Planned Follow-up Observation Period Per Patient:** Patients who have discontinued study treatment without progression will continue to be followed for progression. Every attempt should be made to gather all information every 2 months (radiological scans and survival), even if a patient starts a new anticancer therapy. All patients will be followed until death. Patients who have entered the treatment extension period will be followed for just 30 days after treatment discontinuation.

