**Statistical Methods:**

Statistical: Approximately 120 patients will be randomly allocated to treatment in a 1:2:1 ratio (LY2157299 monotherapy/LY2157299 plus sorafenib therapy/sorafenib plus placebo therapy). This will provide about 83% power (strong prior) to detect a significant treatment difference in terms of OS between the LY2157299 plus sorafenib and sorafenib plus placebo using a Bayesian-augmented control design with a 1-sided alpha of 0.14 under the assumption that the true HR is 0.667 in favor of the LY2157299 plus sorafenib arm.

Efficacy: The primary analysis is to compare the OS between LY2157299 plus sorafenib with sorafenib plus placebo using a Bayesian OS model that augments current control data with additional information from historical data. The same Bayesian OS model will be used to estimate the HR between LY2157299 monotherapy and sorafenib plus placebo. HRs between the 3 treatment arms will also be estimated for TTP and PFS using proportional hazards models. ORR based on the RECIST v1.1 and mRECIST criteria will be calculated.

Safety: Summary statistics, plots, and listings for all safety data collected will be provided by arm.

Health Outcomes: Summary descriptive statistics by study part will be provided for the PRO data (ie, EORTC QLQ-30 and QLQ HCC-18) at each time point and change from baseline. Time to symptomatic progression will also be evaluated.

Pharmacokinetics: A population PK analysis will be performed on all patients receiving LY2157299. A PK analysis will be performed for sorafenib as well. This analysis will explore the impact of covariates such as demographic factors and markers on the relevant PK parameters.

Pharmacodynamics: Changes in response biomarkers, such as phosphorylated SMAD in tumor tissue (or other TGF- $\beta$ -related biomarkers), AFP L3, and E-cadherin in serum will be estimated and may be correlated with clinical efficacy. Exploratory population PK/pharmacodynamic analyses may be conducted to identify the exposure-biomarker response relationship.

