**Figure JBAS.8.2. JBAS extension period design.**

## 8.2. Discussion of Design and Control

Approximately 150 patients will be entered in order to randomly assign 120 patients to 1 of 3 treatment arms using a 1:2:1 allocation ratio in favor of the LY2157299 plus sorafenib arm. A randomized, controlled design is being used in this study. Randomization minimizes systematic

bias in the selection and assignment of patients to study therapy and provides justification for inferential statistical methods to be used on data from this study. The study will use a dynamic allocation method, introduced by Pocock and Simon (1975) (and extended for unequal treatment group sizes by Han et al. [2009]) to minimize imbalance between treatment arms according to factors such as AFP and portal vein thrombosis. Using an appropriate concurrent control arm (which is sorafenib in combination with placebo) enables direct statistical estimation of benefits and harms due to study therapy and minimizes bias in the assessment and interpretation of observed treatment effects. The rationale behind favoring the combination arm in the randomization is that this is the primary treatment of interest to compare with sorafenib alone. However, based on the longer time to progression observed in Study JBAK patients in whom LY2157299 was administered as a monotherapy in a first-line setting, there is medical need of getting more information for efficacy and safety of LY2157299 monotherapy. Therefore, a monotherapy arm is also included and will inform future Phase 3 development. The purpose of the monotherapy arm is to provide a comparison to assess the safety of LY2157299 compared to sorafenib. This is especially important because LY2157299 has shown preclinical cardiac toxicity, which, thus far, has not confirmed in clinical studies. However, sorafenib has known cardiac toxicity in patients. The 3-arm study will provide a better differentiation between the various safety profiles and inform the design of Phase 3. Since OS is not affected by pseudoprogression evaluations, OS is a preferred primary endpoint over TTP or PFS. A Bayesian design can be used to leverage survival data for sorafenib alone from historical clinical trials to benefit from the 2:1 randomization of the combination arm relative to sorafenib alone with the goal of increasing power over an otherwise similar design.

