6.1. General Considerations

This plan describes a priori statistical analyses for efficacy and safety that will be performed according to Protocol version 1.0 dated November 18, 2013. Additional exploratory analyses of the data not described in this plan will be conducted as deemed appropriate.

Statistical analysis of this study will be responsibility of both Quintiles (under the direction of Eli Lilly and Company [Lilly]) and Lilly.

The interpretation of the study results will be the responsibility of the investigator with the Lilly Clinical Research Physician (CRP), pharmacokineticist, and statistician.

Patients from all sites will be pooled for the purposes of analysis. Inference about survival will be made using a Bayesian posterior probability for the superiority of LY2157299 plus sorafenib arm survival over sorafenib plus placebo arm. The remaining analyses of this study will estimate differences between arms where appropriate, including exploratory analyses. Descriptive statistics by treatment arm will also be provided.

Results of descriptive analyses and estimates from inferential analyses will be presented by treatment arm. For continuous variables, summary statistics will include number of patients, mean, median, standard deviation, minimum, and maximum. Categorical endpoints will be summarized using number of patients, frequency, and percentages. Any missing longitudinal data will not be imputed, but rather will be estimated from an appropriate random mixed-effects model. Transformations will be applied where assumptions behind any analysis are better satisfied by data being transformed onto an alternative scale. All results from any of these analyses will be back transformed to the original scale. Alternatively, nonparametric methods will be applied.

Any change to the data-analysis methods described in the protocol will require an amendment ONLY if it changes a principal feature of the protocol. Any other change to the data-analysis methods described in the protocol, and the justification for making the change, will be described in the clinical study report. Additional exploratory analyses of the data will be conducted as deemed appropriate.

The following terms and data handling conventions defined in [Table JBAS.6.1](#) will be used in the analysis.

Table JBAS.6.1. Data Handling Conventions

Term	Definitions or Rule
Entered	Patients who have signed the informed consent document directly.

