A treatment emergent AE (TEAE) is any AE initially occurring after 1st dose; or if initially occurring pre-dose and ongoing at time of first dose (may be a pre-existing condition or AE) and severity of the reoccurrence is greater than the max severity pre-dose; then the reoccurrence is a TEAE. The time frame post-dose includes end of short term follow up period. The CTC LLT will be used to compare pre-dose and post-dose events in the TEAE algorithm.

1. Compare the post-dose LLT with LLT of preexisting conditions/AEs ongoing at first dose:
 - a. If the post-dose LLT is not present as a pre-dose term, then the AE is a TEAE
 - b. If the LLT is present as a pre-dose term AND the severity increases post-dose compared with the most severe pre-dose grade for the same LLT, then the event is a TEAE
2. Time frame post-dose includes end of short term follow up period – that is, 30 days post discontinuation of study treatment.

Treatment-emergent AEs excludes any AE which maps to a LLT recorded at baseline and has the same or lower severity as that at baseline, even if considered drug related or serious.

Treatment-related AEs are events considered as having at least a suspected relationship to the study drug as entered on the CRF.

If the severity grade or relationship to the study drug of an AE is missing, a worst-case scenario will be assumed (that is, Grade 4 or related for post-dose AEs, and Grade 1 or not related for pre-dose AEs).

Specifically, the following summary tables will be provided:

- An overview of AEs including the number and percentage of patients with ≥ 1 TEAE, ≥ 1 CTCAE Grade 3/4, ≥ 1 SAE, who discontinued study treatment due to AE, discontinued study treatment due to SAE, died due to AE on study treatment, and died due to AE within 30 days of discontinuation from study treatment. Additionally, the number of AEs related to study treatment in each of the previous categories will be given.
- The number and percentage of patients experiencing the following TEAEs by treatment group, SOC and PT:
 - TEAEs
 - Related and regardless of relatedness to study drug
 - TEAEs leading to discontinuation from study treatment
 - TEAEs leading to discontinuation from study treatment by serious criteria
 - Related and regardless of relatedness to study drug
 - SAEs
 - TEAEs by maximum reported CTCAE grade
 - Related and regardless of relatedness to study drug
 - TEAEs grouped by maximum CTCAE grade (Any grade, Grades 1/2, Grades 3/4/5, Grade 5)

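### The protocol's Fisher comparison of AE incidence is not carried into the SAP, which specifies no AE contrast, and neither document allows for unequal time under observation

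*Protocol*

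**What the plan says.** **Protocol.** Section 12.2.11 plans an overall AE summary, once for events judged possibly related and once regardless of causality, and adds: "Incidence rates of these events will be compared between treatment arms using" Fisher's exact test. It gives no significance level, does not say which pairs of arms are meant, and makes no allowance for time at risk. The synopsis promises less: "Summary statistics, plots, and listings for all safety data collected will be provided by arm".

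**SAP.** Section 6.12.2 lists an AE overview, then "The number and percentage of patients experiencing the following TEAEs by treatment group, SOC and PT", laboratory grades by visit, shift tables and listings. It names no Fisher test, risk difference, ratio or interval for AEs. The nearest provision is general, in SAP 6.1: "The remaining analyses of this study will estimate differences between arms where appropriate, including exploratory analyses". That sentence names no AE method.

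**Why the arm is there.** Protocol 8.2 states: "The purpose of the monotherapy arm is to provide a comparison to assess the safety of LY2157299 compared to sorafenib". The same paragraph also gives a wider reason: "there is medical need of getting more information for efficacy and safety of LY2157299 monotherapy".

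**Observation time.** Treatment has no fixed length. The synopsis says "Patients will receive LY2157299 until their disease has progressed, the patient has died, or the patient discontinues for adverse events", among other reasons. Under SAP 6.12.2 the treatment-emergent window closes 30 days after study treatment stops. Exposure, cycles completed and dose intensity are summarised descriptively (Protocol 12.2.11, SAP 6.12.1.3) but are not linked to AE incidence.

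**The concern.** There are two separate problems.

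First, the documents disagree. A programmer working from the SAP would not produce the comparison that the protocol promises, nor any other numerical contrast of AEs between arms. The reader of the report would be left to subtract percentages by eye for the comparison that Protocol 8.2 asks for.

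Second, neither version allows for how long patients are watched. The window for counting an AE is time on treatment plus 30 days, so an arm treated for longer has more chance to record a first event at the same underlying rate. Protocol 7.3.1 adds an arm-specific element: patients who stop sorafenib for toxicity may stay on LY2157299 or placebo, which keeps the window open in Arms 2 and 3 and has no counterpart in Arm 1.

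At stake is what the trial can say about monotherapy against sorafenib, and about the combination against sorafenib, when it informs Phase 3.

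**Working it through.** **Plan's own figure.** None exists. Neither document states an alpha, a power or an AE rate for the safety comparison, so what follows is illustration under stated assumptions.

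**Inputs from the documents**
- Arm sizes 30, 60 and 30 (Protocol 12.1).
- Median time to progression (TTP) on LY2157299 monotherapy in sorafenib-naïve patients: 18.3 weeks (Protocol 5.2).
- Median TTP on sorafenib in the Asia-Pacific placebo-controlled trial: 2.8 months (Protocol 5), or 2.8 × 4.348 = 12.2 weeks.
- Window extension after stopping: 30 days, or 30/7 = 4.29 weeks.

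**Assumptions.** The AE hazard λ is constant and equal in both arms, at 0.01 to 0.04 per week. Time on treatment is exponential, with median TTP as a rough proxy for its median. Fisher's test is two-sided at 5%.

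**Step 1: crude incidence with no true difference.** With μ = ln 2 / median,

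p = 1 − exp(−λ × 4.29) × μ / (μ + λ).

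For λ = 0.02:
- Median 18.3 weeks: μ = 0.0379, so p = 1 − 0.918 × 0.654 = 39.9%.
- Median 12.2 weeks: μ = 0.0568, so p = 1 − 0.918 × 0.740 = 32.1%.

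| λ per week | Monotherapy (18.3 wk) | Control (12.2 wk) | Difference (points) | Risk ratio | Fisher rejects, 30 v 30 |
|---|---|---|---|---|---|
| 0.01 | 24.2% | 18.5% | 5.7 | 1.31 | 4.3% |
| 0.02 | 39.9% | 32.1% | 7.8 | 1.24 | 5.6% |
| 0.04 | 59.0% | 50.6% | 8.5 | 1.17 | 6.2% |

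Differences are taken before rounding. The true rate ratio is 1 in every row.

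**Step 2: the direction can reverse.** If monotherapy exposure is shorter, with assumed medians of 8 v 16 weeks, crude incidence is 14.1% v 22.2%, 25.4% v 37.2% and 42.4% v 56.2%. Monotherapy now looks 8 to 14 points safer with no true difference, and Fisher rejects in 7% to 13%. At assumed medians of 10 v 30 weeks the gap is 17 to 23 points, and Fisher rejects in 23% to 33%.

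**Step 3: a real excess can be hidden.** Let the true rate ratio be 2 (0.04 v 0.02 per week) with medians of 8 v 16 weeks. Crude incidence is 42.4% v 37.2%. With both medians at 16 weeks it would be 56.2% v 37.2%.

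**Step 4: what Fisher's test can show at 30 v 30.** The rejection probability is the sum of binomial probabilities over all tables with p ≤ 0.05.
- Size at a common incidence of 10%, 30% and 50%: 0.9%, 2.6% and 2.7%.
- Power for 5% v 20%: 24%. For 10% v 30%: 37%. For 20% v 50%: 60%.

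A non-significant result would therefore be weak evidence of similar safety.

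**The case against.** The other side has real substance.

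- **Crude incidence is a legitimate quantity.** It is the cumulative risk per patient under treatment as given. The synopsis promises only summaries by arm, and the secondary objective is to evaluate safety, not to test it.
- **Other provisions exist.** SAP 6.1 allows differences to be estimated where appropriate. Both documents let changes to non-principal methods be explained in the study report. Protocol 8.2 stresses cardiac toxicity, and SAP 6.12.7 has its own ECG change summaries and echocardiographic shift tables.
- **The remedy is imprecise too.** For 10% v 30% at 30 per arm, the standard error is √(0.1×0.9/30 + 0.3×0.7/30) = 0.10, so the 95% interval for the difference runs from about 0 to 40 points. Patient-year rates assume a roughly constant hazard and can mislead when AEs themselves end treatment.

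All of this stands and limits the point, but none of it supplies an AE contrast or resolves the mismatch. An interval at least shows the imprecision that a bare p-value or percentage hides.

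Some stronger readings are tempting and should be resisted.

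- **That the SAP removed the test.** Its revision history lists the main changes from Version 1 to Version 2, and Version 1 is not available. Nothing shows that the SAP ever contained the test.
- **That the design expects longer exposure in the better arm, so an effective arm must look more toxic.** The hazard ratio of 0.667 in Protocol 12.1 is a survival assumption for the combination arm. The same list assumes a ratio of 1 for monotherapy against control.
- **That a non-significant result will be read as proof of safety.** Neither document says so.

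**Conclusion.** The point holds as a mismatch and a gap, and is worth correcting. The protocol plans an unadjusted Fisher comparison. The SAP omits it and specifies no AE contrast beyond a general sentence. Neither document deals with unequal observation time in a trial where comparing safety with sorafenib is a stated purpose of one arm.

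The size is illustrative: about 6 to 9 points of crude difference with equal hazards at the TTP proxies, and 37% Fisher power for 10% v 30% at 30 per arm. These figures rest on constant, equal AE hazards, exponential time on treatment and a 5% two-sided level, none of which the documents give. The proxies are weak. The 18.3-week figure comes from 20 patients with a 90% interval from 6.3 weeks to not estimable (Protocol 5.1.5.1), and Protocol 10.1 lets patients stay on treatment after objective progression.

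A reader might infer that the safety comparison is confounded, or missing altogether. The documents do not support that. The arms are randomised, so the issue is unequal observation after randomisation, and its size and direction depend on exposure not yet known. At the TTP proxies Fisher's false-positive rate stays near nominal (4% to 6%), so the weight falls on the distorted point estimate and the low power. Safety is also not the arm's only rationale, since Protocol 8.2 cites efficacy information as well.

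**What to change.** Reconcile Protocol 12.2.11 with SAP 6.12.2 so that both name the same analysis. The simplest way is to replace the Fisher sentence with the estimates below and to keep the crude numbers and percentages.

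For the AE overview rows (any treatment-emergent event, Grade 3/4, serious, related, leading to discontinuation), report for Arm 1 v Arm 3 and Arm 2 v Arm 3:

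1. the risk difference with a 95% confidence interval;
2. the incidence of first events per patient-year at risk in each arm, with the rate ratio and a 95% confidence interval. Time at risk runs from first dose to the first event or the end of the treatment-emergent window, and ends earlier at death or data cut-off.

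Name the interval methods in the SAP, and present the results as estimates without significance claims.

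The cost is a few extra table columns. The AE onset, first-dose and discontinuation dates are already collected (SAP 6.12.1 and 6.12.2). The rates assume a roughly constant hazard; keeping the crude percentages beside them limits that drawback. Treatment, sample size and the primary analysis are unaffected.
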